4.1.2 Exclusion Criteria

Individuals who meet any of these criteria are not eligible for enrollment as study participants:

- 1. Inability or unwillingness of a patient to give written informed consent or comply with study protocol
- 2. History of graft loss from acute rejection within 1 year after any previous kidney transplant
- 3. History of previous liver, heart, pancreas, or lung transplant
- 4. History of cellular rejection of current allograft prior to enrollment
- 5. Serum BK virus ≥500 copies/mL by PCR at the time of study entry
- 6. Female subjects who are pregnant or breast feeding
- 7. Participation in any other studies with investigational drugs or regimens in the preceding year from the time of study entry
- 8. Any condition or prior treatment which, in the opinion of the investigator, precludes study participation
- 9. Patients requiring the use of azathioprine or mTOR inhibitors
- 10. Patients with active peptic ulcer disease

5. Investigational Agent: Envarsus

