3.1. Description of Study Design

This will be a single center prospective case control study. We expect 40% of patients will develop BK viruria, 20% BK viremia, 5% BK viral nephropathy (BKVN). Patients will be managed using standard of care for our center (thymoglobulin induction, tacrolimus/mycophenolate/prednisone). Target tacrolimus level is 8-12 ng/mL for the first 6 months post transplant and 6-9 ng/mL thereafter. BK urine/serum is routinely monitored during the first year post transplant. A population of 100 patients is calculated to show significant difference for p value < 0.05.

Population:

Study Group: Post transplant patients (kidney transplant alone) with standard of care immunosuppression, no prior rejection, prior BK or opportunistic infection, and negative BK screening at post-transplant month 1, who have a tacrolimus concentration/dose of < 1 and a steady state therapeutic level will be eligible. Patients who consent to participate will be converted to Envarsus at 20% reduction in tacrolimus dose.

Control Group: Post transplant patients (kidney transplant alone performed between 10-2016 and time of consideration for study control group) with standard of care immunosuppression, no prior rejection, prior BK or opportunistic infection, who had a negative BK screening at post-transplant month 1 and tacrolimus concentration/dose of < 1 at post-transplant month 1, and BK data available for months 2, 3, 6, 9, 12 post transplant.

Study visits: Post-transplant Months 2, 3, 6, 9, 12

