9.1. Enrollment

The research study will be explained in lay terms to each potential research participant. The potential participant will sign an informed consent form before undergoing any study procedures. A participant is considered enrolled in the trial once the consent form has been signed.

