11.7. Reporting of Other Safety Information

An investigator shall notify the site IRB according to the site's IRB guidelines when an "unanticipated problem involving risks to participants or others" is identified, which is not otherwise reportable as an adverse event.

12. Statistical Considerations and Analytical Plan

This is a single center prospective study comparing incidence of BK infection in rapid metabolizers converted from tacrolimus to Envarsus against a recent historical control of rapidly metabolizing recipients who had BK screening at similar points, but remained on tacrolimus.

This study has both safety and efficacy endpoints.

We will use standard descriptive statistics for continuous and categorical data to define adverse events, and clinical outcomes as noted above. Analysis will be undertaken utilizing UAB statistical support in the School of Public Health and Transplant Quality, Informatics and Outcomes.

The enrollment plan is based on a power calculation. A population of 100 patients is calculated

to show significant difference for p value < 0.05.

Our results will be submitted to national/international nephrology/transplant meetings, and as a primary manuscript reporting the primary efficacy and safety data, and secondary manuscripts reporting different secondary endpoints, as appropriate.

We expect the changes over time in these assays to be approximately linear. If after examination of the data, this appears to not be the case, then we will either transform the assay measures or model the time axis time points as an unordered factor (similar to repeated measures ANOVA, but without the requirement for fully balanced data).

We will use descriptive analyses to summarize subject characteristics of our study population. Dichotomous variables will be summarized as proportions with 95% confidence intervals. Continuous variables will be summarized using means, standard deviations, and 95% confidence intervals if they are symmetric and unimodal. Otherwise, they will be summarized using the median and the interquartile range. Simple t-, chi-squared, or Fisher's exact test, as appropriate, will be used to compare quantitative measures across treatment groups. The following variables will be summarized:

- Baseline and demographic characteristics
- Use of concomitant medications
- Reasons for early termination
- All reportable AEs

No formal interim analyses of this study are planned.

13. Identification and Access to Source Data

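### Several exclusions applied to Envarsus patients, including early rejection loss of a previous kidney and the investigator's veto, are not stated for the historical controls, so baseline risk may differ

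*Combined protocol and SAP*

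**What the plan says.** The two groups are selected under different parts of the protocol.

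**Envarsus patients.** Section 4.1.2 states: "Individuals who meet any of these criteria are not eligible for enrollment as study participants". Section 9.1 says what enrolment means: "A participant is considered enrolled in the trial once the consent form has been signed". No consent step is described for historical controls, so on its own terms the list governs the prospective Envarsus patients. It includes:

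- item 2: "History of graft loss from acute rejection within 1 year after any previous kidney transplant"
- item 3: a previous liver, heart, pancreas or lung transplant
- item 4: "History of cellular rejection of current allograft prior to enrollment"
- item 7: investigational treatment in another study during the preceding year
- item 8: "Any condition or prior treatment which, in the opinion of the investigator, precludes study participation"

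Section 4.1.1, item 2, requires age 18 or over.

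**Controls.** Section 3.1 defines them separately: "Post transplant patients (kidney transplant alone performed between 10-2016 and time of consideration for study control group) with standard of care immunosuppression", with "no prior rejection, prior BK or opportunistic infection, who had a negative BK screening at post-transplant month 1". They also need a tacrolimus concentration/dose ratio below 1 at month 1 and BK results at months 2, 3, 6, 9 and 12.

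**Analysis.** Section 12 describes a recent historical control and says: "Simple t-, chi-squared, or Fisher's exact test, as appropriate, will be used to compare quantitative measures across treatment groups". It mentions no matching or covariate adjustment. Section 3.4 lists rejection, graft failure, graft dysfunction and proteinuria as secondary endpoints.

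**The concern.** Without randomisation, matching or adjustment, eligibility is the only stated means of making the groups comparable, so it should be the same on both sides. Exclusion 2 selects directly on immunological history. Exclusion 8 is discretionary and can remove anyone judged unsuitable. A person picking controls from charts under 3.1 has no instruction to apply either.

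Rejection and graft failure are the endpoints through which this study would show harm to the graft after conversion. If patients at higher risk are removed from the Envarsus side only, the control rejection rate is raised for reasons unrelated to the drug, and a real Envarsus excess could be partly hidden.

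**Working it through.** The plan gives no figure of its own on this point, and its sample size of 100 does not enter. The check has three steps.

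**Step 1. Criteria side by side.**

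| Criterion (4.1.1 and 4.1.2) | Counterpart in the control definition (3.1) |
|---|---|
| Age 18 or over | None stated |
| Exclusion 2, early rejection loss of an earlier kidney | None explicit; the bar on prior rejection does not say whether it reaches earlier grafts |
| Exclusion 3, previous other-organ transplant | None; kidney alone describes the current operation |
| Exclusion 4, rejection of the current graft | Covered by the bar on prior rejection, but with no index date |
| Exclusion 7, recent investigational treatment | None stated |
| Exclusion 8, investigator veto | None stated |
| Exclusion 9, azathioprine or mTOR inhibitors | Largely covered by standard-of-care immunosuppression |
| No such entry condition | BK data at months 2, 3, 6, 9 and 12 |

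The index date in the fourth row matters. Exclusion 4 runs up to enrolment, which may be as late as 8 weeks after transplant. If controls are judged at month 1, a rejection between month 1 and week 8 disqualifies an Envarsus candidate but could count as a control event.

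**Step 2. Rejection.** Let *b* be the risk in patients who meet all criteria, *s* the share of controls who would fail an Envarsus-only criterion, and *k* their relative risk. With no drug effect:

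control rate = b(1 − s) + b·s·k, so the excess over *b* is b·s·(k − 1).

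For *b* I use two values: 15%, the midpoint of the 14% and 16% in the de novo trial described in 2.4.1, and 2.5%, the tacrolimus-arm biopsy-proven rate in the conversion trial described in 2.4.2. The documents give neither *s* nor *k*; I assume 5% to 15% and 2 to 3.

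| b | s | k | Control rate | Excess (points) |
|---|---|---|---|---|
| 15% | 5% | 2 | 15.75% | 0.75 |
| 15% | 10% | 2 | 16.5% | 1.5 |
| 15% | 15% | 2 | 17.25% | 2.25 |
| 15% | 15% | 3 | 19.5% | 4.5 |
| 2.5% | 5% | 2 | 2.625% | 0.125 |
| 2.5% | 15% | 3 | 3.25% | 0.75 |

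The range is about 0.1 to 4.5 points. Milder inputs (b = 16%, s from 1% to 10%, k from 1.5 to 3) give 0.08 to 3.2 points.

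**Step 3. Graft failure.** Section 2.4.1 gives 96% graft survival on tacrolimus at 12 months, so b = 4%. The same *s* and *k* add 4 × 0.05 × 1 = 0.2 to 4 × 0.15 × 2 = 1.2 points to the control rate.

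The month-12 data condition works the other way. If a share *f* of control graft failures lack complete BK data and drop out of the pool, the observed rate is b(1 − f)/(1 − b·f):

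- f = 25%: 3.0/0.99 = 3.03%, a change of −0.97 points
- f = 50%: 2.0/0.98 = 2.04%, a change of −1.96 points
- f = 100%: 0%, a change of −4.0 points

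To combine the two effects, let *c* be the raised control rate, 4.2% to 5.2%. They cancel when c(1 − f)/(1 − c·f) = b, that is, f = (c − b)/[c(1 − b)]:

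- c = 4.2%: 0.002/(0.042 × 0.96) = 0.05
- c = 5.2%: 0.012/(0.052 × 0.96) = 0.24

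So if more than about 5% to 24% of control graft failures are lost through the data condition, the net bias favours the controls. The documents do not give *f*.

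**The case against.** The strongest reply is that controls are already screened for immunological risk. Section 3.1 demands no prior rejection of both groups. That is at least as broad as exclusion 4 and, unqualified, might be read to reach exclusion 2. Standard-of-care immunosuppression largely takes care of exclusion 9. This stands: a reader who infers that immunological exclusions are never applied to controls goes too far. The documents are silent on items 2, 3, 7 and 8 and the age limit; they do not forbid applying them. But silence leaves control selection without a rule.

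The size is also open to attack. The 15% rate comes from de novo patients and counts clinically suspected and treated rejection, whereas patients here must be rejection-free at entry. The conversion trial enrolled stable patients, so its 2.5% is a low anchor rather than a match. Items 7 and 8 and age have no documented link to rejection, and nothing suggests that under-18s are in the control pool. All of this stands, and it is why only a wide, assumed range can be given.

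The sentence on simple tests in section 12 introduces a list of baseline characteristics, medications, terminations and adverse events, and does not name rejection or graft failure. Summarising baseline characteristics may expose some imbalance. However, no other method is stated for these endpoints, and showing an imbalance does not correct for it.

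A reader might also infer a bias in the primary BK endpoint, on the idea that the unexcluded controls are more heavily immunosuppressed. The documents do not support that: 3.1 puts both groups on the same standard-of-care regimen at one centre.

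**Conclusion.** The asymmetry is real. Exclusions 2, 3, 7 and 8 and the age limit bind consented Envarsus patients, are not in the control definition, and are not offset by matching or adjustment.

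For rejection, this taken alone plausibly favours Envarsus by about 0.1 to 4.5 points. That rests on an assumed baseline rate of 2.5% to 15%, 5% to 15% of controls affected and a two- to threefold risk. The month-12 data condition offsets rejection less clearly than graft failure, because a treated rejection need not interrupt BK monitoring.

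For graft failure, it is tempting to conclude that the Envarsus group starts at lower risk. The documents do not establish that: the control-only data condition pushes the other way, and the net direction is unknown.

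The point concerns secondary endpoints. It is modest in size but worth correcting because the correction is cheap.

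**What to change.** In 3.1, require each control to meet, from the chart and at the same post-transplant time point as Envarsus entry, the age limit and exclusions 2, 3 and 7. Date the bar on prior rejection to that same point. For exclusion 8, record the reason each time it is used and apply to controls every reason that a chart can show.

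Do not make that change alone. Also stop requiring complete BK data for months 2 to 12 as a condition of control entry; otherwise one bias is removed while the opposing one stays, and the graft-failure comparison could become worse.

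The cost is a few extra chart fields and the loss of a few controls. Admitting controls with incomplete BK results also means section 12 must say how missing results are handled, in both groups alike.

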4.1. Enrollment Eligibility Criteria

4.1.1. Inclusion Criteria

Individuals who meet all of the following criteria are eligible for enrollment as study participants:

- 1. Patient must be able to understand and provide informed consent
- 2. Age \geq 18 years of age at the time of study entry
- 3. Recipient of a deceased or living donor kidney transplantation
- Maintenance immunosuppression consisting of tacrolimus/MMF/MPA (≥1000 mg/720 mg daily) ± prednisone (≤10 mg/day)
- 5. Patient is less than or at 8 weeks post transplant with a negative serum BK Virus screen at 3-4 weeks post transplant
- 6. Patient has a tacrolimus drug dose/concentration of > 1 with therapeutic tacrolimus levels.
- 7. Women of childbearing potential defined as all women physiologically capable of becoming pregnant, must have reviewed Mycophenolate REMS and have a negative pregnancy test upon study entry.
- 8. Female (and male) subjects with reproductive potential must agree to use a highly effective method of birth control for the duration of the study. Please note that according to the US product information for MMF/MPA, two reliable forms of contraception must be used simultaneously unless female sterilization, male sterilization, post-menopausal status or total abstinence is the chosen method.

Acceptable methods of highly effective birth control include:

- Condom with spermicide
- Diaphragm and sperm ide
- Cervical cap and spermicide
- Use of oral, injected or implanted hormonal methods of contraception or other forms of hormonal contraception that have comparable efficacy (failure rate <1%), for example hormone vaginal ring or transdermal hormone contraction
- Intrauterine device (IUD)

Female sterilization (have had surgical bilateral oophorectomy with or without hysterectomy) or tubal ligation at least six weeks prior to screening.

Male sterilization at least 6 months prior to screening. For female subjects on the study, the vasectomized male partner should be the sole partner for that subject.

Post menopausal women defined as being not of child bearing potential if they have had 12 months of natural (spontaneous) amenorrhea.

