9.2. Follow - Up Visits

The initial visit and subsequent visits on study days 30, 120, 210, and 300 will include routine evaluation with physical examination and laboratory studies. These laboratory studies include BK urine and serum testing, CBC, renal function panel, eGFR, CNI and MPA drug levels, urinalysis, donor specific antibody testing, and urine protein/creatinine ratio according to the center's standard of care.

Please refer to Appendix 1 for schedule of events.

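### Serum BK at or above 500 copies/mL at study entry bars an Envarsus patient but not clearly a control, and the primary endpoint has no stated start of counting

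*Combined protocol and SAP*

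**What the plan says.** **Envarsus group.** Inclusion criterion 5 (4.1.1) reads "Patient is less than or at 8 weeks post transplant with a negative serum BK Virus screen at 3-4 weeks post transplant". Exclusion criterion 5 (4.1.2) adds a second serum test: "Serum BK virus ≥500 copies/mL by PCR at the time of study entry". Section 9.1 defines entry: "A participant is considered enrolled in the trial once the consent form has been signed". Table 1 in 9.4 and Appendix 1 place that at Day 0, about month 2 and within 8 weeks of transplant. Appendix 1 schedules urine and serum BK PCR at the screen, at Day 0 and at every later visit.

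**Control group.** Section 3.1 takes earlier recipients "who had a negative BK screening at post-transplant month 1" and requires "BK data available for months 2, 3, 6, 9, 12 post transplant". It attaches no eligibility rule to the month-2 result. The criteria in 4.1 govern enrolment, and historical controls are not enrolled and have no Day 0.

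**Both groups.** Section 3.1 asks for "no prior rejection, prior BK or opportunistic infection", without a reference date.

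**Endpoint.** Sections 1.3 and 3.3 define a composite of viruria, viremia or nephropathy. Neither they nor Section 12 say when counting starts. Section 3.1 lists "Study visits: Post-transplant Months 2, 3, 6, 9, 12", and 9.2 includes BK testing at "The initial visit and subsequent visits on study days 30, 120, 210, and 300".

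**The concern.** In a comparison with historical controls, both groups need the same eligibility test at the same post-transplant time. Here the Envarsus group appears to be cleared of viremia twice and the controls once. A patient who turns viremic between the two tests is removed from one group and can be scored as an event in the other. That would lower the Envarsus event rate relative to control even if conversion did nothing, and a larger sample would not remove the difference.

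The missing start of counting is a separate matter. It favours neither group by itself. It does allow the primary endpoint to include infection first found at the Day-0 or month-2 test, which conversion could not have prevented.

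**Working it through.** **1. The plan's own figure.** The 100 patients in 3.1 and Section 12 cannot be reproduced, because the documents give no Envarsus-group rate, power, sidedness or allocation. The 50 per group used below is therefore an assumption.

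**2. Which patients are treated differently.** All four are negative at month 1.

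| Status at the entry time | Envarsus | Control |
|---|---|---|
| Serum ≥500 | Barred by exclusion 5 | Not clearly barred; can be counted |
| Viremic in between, below 500 at entry | Only the undated prior-BK clause could bar | Same clause |
| Isolated viruria | Not barred by 4.1.2; can be counted | Same |
| Clear, viremic later | Eligible, event | Eligible, event |

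Only the first row differs between groups. Viruria at month 1 may already be screened out, since Appendix 1 has urine PCR at the screen. The open viruria question then covers cases first appearing between the screen and Day 0.

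**3. Shift with no drug effect.** Section 3.1 expects 40% viruria and 20% viremia. Assumptions: all viremia lies within the 40%, so the composite is 40%; a share f of the viremia is present at entry; f is 5–30%. Removing those patients from the Envarsus group only gives:

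- composite = (0.40 − 0.20f)/(1 − 0.20f)
- viremia = 0.20(1 − f)/(1 − 0.20f)

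For f = 0.05 the composite is 0.390/0.990 = 39.4%. For f = 0.30 it is 0.340/0.940 = 36.2%.

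**4. False-positive rate.** Exact enumeration of the uncorrected chi-squared test, two-sided 0.05, control rate 40%:

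| f | Envarsus composite | Envarsus viremia | Two-sided rejection, 50 per group | False wins for Envarsus, 50 per group | False wins, 100 per group |
|---|---|---|---|---|---|
| equal rules | 40% | 20% | 5.2% | 2.6% | 2.6% |
| 0.05 | 39.4% | 19.2% | 5.3% | 3.0% | 3.1% |
| 0.10 | 38.8% | 18.4% | 5.4% | 3.4% | 3.8% |
| 0.20 | 37.5% | 16.7% | 5.9% | 4.5% | 5.6% |
| 0.30 | 36.2% | 14.9% | 6.9% | 6.0% | 8.1% |

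The composite shift is 0.6 to 3.8 points. The standard error of the difference is √(2 × 0.4 × 0.6/50) = 9.8 points. A 40:60 split either way gives false wins of 2.9–5.9%.

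**5. Power under three counting rules.** Pooled normal approximation, 50 per group, assumed 50% reduction of post-entry events, with f now the share of all composite events present at entry:

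- *Plan as written:* control 0.40. Envarsus is (0.20f + 0.5 × 0.40(1 − f))/(1 − 0.20f) = 0.20/(1 − 0.20f), or 0.202–0.213. Power 58–53%.
- *Serum rule equal, time-zero viruria still counted:* control (0.40 − 0.20f)/(1 − 0.20f), Envarsus 0.20/(1 − 0.20f). Power 56–38%; the true 50% reduction appears as 49–41%.
- *Serum rule equal, counting after time zero, viruric patients kept and assumed to have no later event:* control 0.40(1 − f)/(1 − 0.20f), or 38.4–29.8%. Power 56–43%.

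**The case against.** **The prior-BK clause covers both groups.** It may be meant to exclude controls with month-2 viremia. But it has no date, the only dated BK anchor for controls is month 1, and month-2 data are requested alongside months 3–12 as follow-up. The reference in Section 12 to screening at similar points concerns when tests were done, not who qualifies. The gap is not clearly closed.

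**The Day-0 PCR may not be the gate.** Consent and PCR share Day 0, signing consent enrols the patient, and nothing says the result must be back first. Entry is capped at 8 weeks but may be earlier. If the 3–4 week screen is the latest result used, the groups are filtered at about the same time. This stands, and it limits both size and certainty.

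**Incidence in converted patients already implies new infection after conversion.** That is a natural reading of Section 12, but it sets no date for controls, and 3.1 lists month 2 as a study visit.

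**The size is assumed and small against sampling error.** This also stands: at f = 5–10% two-sided rejection is almost unchanged.

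A reader might infer that any viremia first found after the screen bars an Envarsus patient. Exclusion 5 does not say so; it bars only serum at or above 500 at entry. A reader might also infer a far larger error. If 10–15% of all controls had month-2 viremia as their first event, two-sided error would reach 0.106–0.197. That would put 50–75% of the plan's 20% viremia by month 2, which no passage supports.

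**Conclusion.** The concern holds, with moderate confidence. The eligibility rules differ between groups for patients who are negative at month 1 and have serum BK at or above 500 copies/mL at the entry time. Where entry falls after the screen and a current result is used, the difference favours Envarsus. The effect is small to modest: 0.6 to 3.8 points on the composite and false wins of 3.0–6.0% against 2.6%. These figures rest on the assumed 5–30% share, viremia nested within viruria, a 40% composite and 50 per group.

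It would be too strong to say that the comparison is certainly biased, since the gap can approach zero. The missing start of counting is a real omission without a direction of its own. The point should be fixed before analysis.

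**What to change.** In 3.1, 3.3 and Section 12:

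1. Apply the same serum rule (BK below 500 copies/mL) to controls, at their month-2 test or at a post-transplant time matched to Envarsus entry.
2. Name that test as time zero in both groups (Day 0 for Envarsus), and date the prior-BK clause to it.
3. Count as primary events only BK infection first detected after time zero.
4. Treat viruria already present at time zero identically in both groups. One option is to keep the patient, not count the existing viruria, and count later viremia or nephropathy. Excluding such patients could be a sensitivity analysis.
5. If controls are cleared at month 2 while some Envarsus patients enter earlier, report entry times and check the remaining mismatch, which runs in the opposite direction.
6. Restate the basis for the 100 patients at the event rate after time zero.

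The change is wording only: controls must already have month-2 BK data, and Day-0 PCR is scheduled. The cost is fewer countable events. Under the assumptions above, power is about 56–43%, against 58–53% for the plan as written, part of which comes from the mismatch itself. A 59% baseline (40% against 20%) would overstate the loss, because it treats infections present before conversion as preventable. Once the serum rule is equal, counting from time zero does better than still counting existing viruria (56–43% against 56–38%).
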